### **Study Design, Study Procedures, and Statistical Procedures**

This study is designed as a single center, prospective, randomized controlled study to assess cardiac benefit of SGLT2i in 40 consecutive patients (20 treatment, 20 control) admitted to University of Chicago Cardiac Intensive Care Unit (CCU) Advanced Heart Failure Service. Patients will be randomized to one of two routine care arms: treatment with an SGLT2i (dapagliflozin 10 mg daily) or no SGLT2i. Assuming a power of 80% and alpha of 0.05, 16 patients are needed in each arm of the study to detect a 5 mmHg change in pulmonary capillary wedge pressure (PCWP), and 18 patients are needed in each arm of the study to detect a 0.75 L/min/m^2 change in Fick cardiac index (CI).

Patients  $\geq 18$  years old, with heart failure with reduced ejection fraction (HFrEF), defined as left ventricular ejection fraction (LVEF)  $\leq 40\%$ , who are admitted to the CCU for acute decompensated heart failure and determined to need pulmonary artery catheter in place for continuous hemodynamic monitoring following right heart catheterization, will be included in this study. Patients listed for cardiac transplantation or on mechanical support will be excluded. Due to the inability to consent patients following sedation given during the right heart catheterization,

patients determined to have a high likelihood of needing CCU admission, based on individual clinical presentation, will be approached for recruitment and asked for informed, written consent. However, patients will only be enrolled if it is determined independently to admit the patient to the CCU with the pulmonary artery catheter in place. If determined to need CCU care with continuous pulmonary artery catheter monitoring, patients will then be randomized, in a 1:1 fashion using the random number generation function in Microsoft Excel, to either treatment with an SGLT2i (dapagliflozin 10mg once daily) or no SGLT2i. Therefore, we anticipate recruiting and consenting more than 40 patients, but we will only randomize and treat patients that fulfill all inclusion criteria. Patients consented but not meeting randomization criteria will not have any data collected or change to their management.

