The patient's treating physician will be able to override randomization assignment if the physician determines that the assignment is not in the patient's best interest. These patients would be kept on study and their data would be used for observational research within this study.

Data points to be collected: Leveled invasive hemodynamics measured via pulmonary artery catheter at end expiration, standing weights, intake and outputs, blood glucose from basic metabolic panels (BMP) taken at those time points, HbA1C (if not within 3 months), blood pressure (cuff pressure), vasoactive doses, and renal function (measured by serum creatinine and estimated GFR) will be captured at multiple time points during CCU admission, as described below. All data points collected for use in this study are being measured as part of the patient's routine care.

**(1) Cardiac catheterization lab prior to CCU arrival:** Initial baseline hemodynamics obtained in the cardiac catheterization lab prior to CCU arrival will be collected.

- a) Cardiac index (L/min/m^2) by Indirect Fick Method
- b) Right atrial pressure (RAP) (mmHg)
- c) Pulmonary artery systolic pressure (PASP) (mmHg)
- d) Mean pulmonary artery pressure (mPA) (mmHg)
- e) Pulmonary artery diastolic pressure (PADP) (mmHg)
- f) Pulmonary capillary wedge pressure (PCWP) (mmHg)
- g) Pulmonary artery pulsatility index (PAPI)
- h) Right ventricular stroke work index (RVSWI) (mmHg L m^-2)
- i) Systemic vascular resistance (SVR) (dynes/sec/cm^5)
- j) Pulmonary vascular resistance (PVR) (dynes/sec/cm^5)
- k) Systolic, diastolic, and mean blood pressure (SBP/DBP/MAP) (mmHg)
- l) Aortic pulsatility index (API)

**(2) Hour 0 – Leveled hemodynamics,** repeated within two hours of arrival to CCU bed from cardiac catheterization lab prior to SGLT2i administration/equivalent if randomized to no SGLT2i arm, will be collected. All baseline data points to be collected at this time.

- a. Cardiac index (L/min/m^2)
- b. RAP (mmHg)
- c. PASP (mmHg)

- d. mPA (mmHg)
- e. PADP (mmHg)
- f. PCWP (mmHg)
- g. PAPi
- h. RSVWI (mmHg L m^-2)
- i. SVR (dynes/sec/cm^5)
- j. PVR (dynes/sec/cm^5)
- k. SBP/DBP/MAP
- l. API
- m. Standing weight
- n. Urine output
- o. Blood glucose taken from BMP
- p. HbA1c
- q. Current Vasoactive doses
- r. Renal function (serum Creatinine, serum eGFR)
- s. Total diuretic dose

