(3) **Hour 1** – Following repeat hemodynamics in CCU bed, patients will be given SGLT2i if randomized to SGLT2i arm, or not given SGLT2i if randomized to no SGLT2i arm.

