### **Potential Risks**

SGLT2i have been shown to have beneficial effects on renal function (5,20). However, due to its direct effect on the kidneys, SGLT2i are labeled for patients with eGFR  $\geq 20\text{ml/min}/1.73\text{m}^2$  or GFR  $\geq 30\text{ml/min}/1.73\text{m}^2$  depending on the medication. Due to this, we will exclude patients with eGFR  $< 30\text{ml/min}/1.73\text{m}^2$ . Increased risk of genital mycotic infections (i.e. vaginitis and balanitis), urinary tract infections, pyelonephritis, urosepsis, and perineal necrotizing fasciitis have been reported, but only genital infections have been shown to be a significant risk in large randomized trials (3-5). Additionally, there has been a small increased risk of diabetic ketoacidosis associated with the use of SGLT2i, though this was predominantly in patients on insulin, who will not be included in this study (5). Lastly, canagliflozin was associated with an elevated risk of lower limb amputation and bone fractures compared to placebo in the CANVAS trial, but this was not seen with the CREEDANCE trial of canagliflozin, or in other SGLT2i randomized controlled trials, including the EMPA-REG OUTCOME, DECLARE-TIMI-58, DAPA-HF, EMPEROR-Reduced trials completed for empagliflozin and dapagliflozin (4). We will not be using canagliflozin in this study.

The adverse reactions of dapagliflozin in order of incidence include female genital mycotic infections, nasopharyngitis, urinary tract infection, back pain, increased urination, male genital mycotic infections, nausea, influenza, dyslipidemia, constipation, dysuria, pain in extremity, increase in creatinine, increase in hematocrit, dyslipidemia, hypersensitivity reactions, urosepsis, necrotizing fasciitis of the perineum.

Since patients are randomized to two routine care arms, we do not believe there is additional risk incurred by participating in this study. The treating physician will be notified of the randomization assignment and can override the assignment if they believe it to be in the best interest of the patient. While SGLT2 inhibitor therapy is approved for use in patients with HFrEF, there is not sufficient data guiding its use in the ICU-setting in patients with acute decompensated heart failure. If benefit is shown in the SGLT2i population, the arm without SGLT2i would lose the hypothesized benefit of renal and cardiovascular benefits during the CCU stay.

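### Nothing keeps the open-label allocation from being disclosed before the Hour 0 reading, so arm-aware care could shift the last pre-dose PCWP and cardiac index

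*Combined protocol and SAP*

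**What the plan says.** All of this is in the combined protocol and SAP, mostly under Study Design, Study Procedures, and Statistical Procedures.

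- **Allocation.** "If determined to need CCU care with continuous pulmonary artery catheter monitoring, patients will then be randomized, in a 1:1 fashion". The arms are "treatment with an SGLT2i (dapagliflozin 10 mg daily) or no SGLT2i", so there is no placebo.
- **Disclosure.** Under Potential Risks: "The treating physician will be notified of the randomization assignment and can override the assignment". No time is given for the notification.
- **Catheterization-lab set, item (1).** "Initial baseline hemodynamics obtained in the cardiac catheterization lab prior to CCU arrival will be collected". It includes PCWP and cardiac index by the indirect Fick method.
- **Hour 0 set, item (2).** The hemodynamics are "repeated within two hours of arrival to CCU bed from cardiac catheterization lab prior to SGLT2i administration/equivalent if randomized to no SGLT2i arm", followed by "All baseline data points to be collected at this time". The list adds vasoactive doses and total diuretic dose.
- **Hour 1, item (3).** "Following repeat hemodynamics in CCU bed, patients will be given SGLT2i if randomized to SGLT2i arm".
- **Reading.** At the end of the data-collection schedule, a picture of the measurement goes to a heart failure attending who is outside the patient's care and blinded to treatment.
- **Outcomes.** The primary outcome is change in indirect Fick cardiac index and change in PCWP. Neither the starting point nor the follow-up time of the change is named.

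**The concern.** Randomisation balances what is measured before the arm can influence anything. A baseline recorded after staff know the arm loses that protection. According to the Study Subjects section these patients require vasoactive support, and the protocol does not standardise vasoactive or diuretic treatment between the catheterization lab and Hour 0. A physician who knows that one patient is about to receive a drug expected to cause natriuresis, and another is not, may treat the two differently in the meantime.

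Blinded interpretation does not help here. It protects the reading of the tracing, but if care has differed, the true pressure has already moved. The recorded data would not settle the matter either. Doses are listed at Hour 0 but not in the catheterization-lab set, and the time of disclosure is not among the data points. An imbalance in doses at Hour 0 could not be dated to before or after disclosure.

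At stake is the starting point of both primary outcomes in a trial of 40 patients.

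**Working it through.** **1. Order of events.** The allocation sentence ties randomisation to the decision for CCU care with the catheter, which follows the right heart catheterization. Hour 0 comes after transfer, up to two hours after arrival in the CCU bed, and its wording already refers to patients randomised to no SGLT2i. The Hour 1 item describes only giving or not giving the drug; it mentions no draw between Hour 0 and Hour 1. The natural order is therefore allocation, then Hour 0, then first dose. The text does not fix this order, and allocation between Hour 0 and Hour 1 would also fit.

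**2. What can act on Hour 0.** The drug is given after Hour 0, so it cannot. An override changes whether the drug is given, again after Hour 0, so it cannot move an Hour 0 pressure. What remains is co-treatment, or timing of the reading, chosen with the arm known.

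**3. The plan's own figures.** It states 16 per arm for 5 mmHg and 18 per arm for 0.75 L/min/m², with 80% power and alpha 0.05, and gives no SD. With n = 2(1.960 + 0.842)² × SD²/difference²:

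- PCWP, SD 5 mmHg: 2 × 7.85 × (5/5)² = 15.7, rounded up to 16.
- Cardiac index, SD 0.8: 2 × 7.85 × (0.8/0.75)² = 17.9, rounded up to 18.

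The stated numbers are attainable but cannot be verified. They imply an SD of about 4.7 to 5.0 mmHg and 0.76 to 0.80 L/min/m² if two-sided, or 5.4 to 5.7 and 0.86 to 0.90 if one-sided. SDs of 5 and 0.8 are used below as assumptions for the SD of the change.

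**4. How a shift carries over.** Suppose arm-aware care moves mean Hour 0 PCWP in one arm by s, and a fraction p of that remains at follow-up. The change-score contrast moves by (p − 1)s. If nothing remains (p = 0), it moves by the full s. If all remains (p = 1), it does not move. The direction depends on the arm: lower Hour 0 PCWP in the treated arm hides part of a true fall, while lower Hour 0 PCWP in the control arm exaggerates it. The protocol names no analysis model. With baseline adjustment and an assumed slope of 0.5, a shift of 1 mmHg that fades would move the contrast by 0.5 × 1 = 0.5 mmHg, or 10% of the target.

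**5. Illustration.** Change score, 20 per arm, two-sided t-test at 0.05, shift fully faded. The standard error is SD × √(2/20): 1.58 mmHg for PCWP and 0.253 L/min/m² for cardiac index. For a 1 mmHg shift the noncentrality is 1/1.58 = 0.63 with no true effect, and (5 − 1)/1.58 = 2.53 when the shift works against a true 5 mmHg effect.

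| Assumed shift | Share of target | Rejection rate, no true effect | Power, shift against the target effect |
|---|---|---|---|
| PCWP none | 0% | 5% | 87% |
| PCWP 0.5 mmHg | 0.5/5 = 10% | 6.1% | 79% |
| PCWP 1 mmHg | 1/5 = 20% | 9.5% | 69% |
| PCWP 2 mmHg | 2/5 = 40% | 23.4% | 46% |
| CI none | 0% | 5% | 82% |
| CI 0.05 L/min/m² | 0.05/0.75 = 6.7% | 5.4% | 77% |
| CI 0.1 L/min/m² | 0.1/0.75 = 13.3% | 6.7% | 71% |
| CI 0.2 L/min/m² | 0.2/0.75 = 26.7% | 12.0% | 56% |

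Every shift in the table is assumed. The documents give no information on the size, or the existence, of a real one.

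**The case against.** The strongest reply is that the protocol never says the arm is known at Hour 0. It gives no time for the draw or the notification, and the Hour 0 reference to the no-SGLT2i arm may only identify the control equivalent of the dosing time. That is correct, and a reader who infers that Hour 0 is definitely measured after disclosure goes further than the text. What stands is that the protocol allows that order and reads most naturally that way.

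Second, Hour 0 is not declared the baseline for the primary outcomes. The catheterization-lab set is also called baseline, contains both measures, and names the indirect Fick method, whereas the Hour 0 list names no method for cardiac index. This too is correct. Still, Hour 0 is the clock origin and the last set before dosing. The catheterization-lab list has no weight, glucose, renal function or vasoactive dose, so for change in those secondary outcomes Hour 0 is the only scheduled pre-dose set. The catheterization-lab values are also taken around sedation and before transfer, which makes them an imperfect replacement.

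Third, re-ordering protects only the baseline. Open-label vasoactive and diuretic management continues from Hour 0 through Hour 27 and possibly to Hour 75, and that route remains open. This limits what the change achieves, but is no reason to leave an avoidable route open as well.

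**Conclusion.** The point holds as a preventable weakness in the order of procedures. The protocol permits, and on its natural reading implies, that the treating physician knows the arm for up to two hours of CCU care before the last pre-dose PCWP and cardiac index are recorded. It also leaves open which set the change is measured from.

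Its size cannot be estimated from the documents. Under the assumptions above, even 1 mmHg would take up a fifth of the target difference.

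Three stronger readings are not supported:

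- That every early difference between arms biases the result. One that persists to follow-up cancels in a change score.
- That the override distorts the baseline. It acts on dosing, which comes later.
- That a bias of a particular size is present. Nothing in the documents shows that care does differ before Hour 0.

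The change is worth making because it closes the route by design and does not alter the sample size.

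**What to change.** 1. State that the allocation is drawn and disclosed only after the complete Hour 0 set has been recorded (tracing picture, cardiac index, vasoactive and diuretic doses), and before the Hour 1 step.
2. Name Hour 0 as the baseline for change in cardiac index and in PCWP, and state that the Hour 0 cardiac index is by the indirect Fick method given in the Outcomes section.
3. Record the clock times of disclosure and of the Hour 0 reading, so that departures can be identified.
4. For any patient whose arm was disclosed before Hour 0, run a sensitivity analysis with the catheterization-lab values as baseline, and note in the report that these are taken around sedation and before transfer.

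The cost is a change in protocol wording and two time stamps, with no extra patients or hemodynamic measurements. The practical downside is a short window between Hour 0 and Hour 1 in which to allocate, notify the physician and prepare the first dose. Differences in open-label care after Hour 0 remain and need their own handling.

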#### (4) **Hour 3**

- a. Cardiac index (L/min/m^2)
- b. RAP (mmHg)
- c. PASP (mmHg)
- d. mPA (mmHg)
- e. PADP (mmHg)
- f. PCWP (mmHg)
- g. PAPi
- h. RSVWI (mmHg L m^-2)
- i. SVR (dynes/sec/cm^5)
- j. PVR (dynes/sec/cm^5)
- k. SBP/DBP/MAP
- l. API
- m. Standing weight
- n. Urine output
- o. Blood glucose taken from BMP
- p. HbA1c
- q. Current Vasoactive doses
- r. Renal function (serum Creatinine, serum eGFR)
- s. Total diuretic dose

(5) **Hour 27** - 2 hours after 2nd dose of SGLT2i, which will be administered 24 hours after first dose, or equivalent time period after which the dose would have been given for the No-SGLT2i arm.

- a. Cardiac index (L/min/m^2)
- b. RAP (mmHg)
- c. PASP (mmHg)
- d. mPA (mmHg)
- e. PADP (mmHg)
- f. PCWP (mmHg)
- g. PAPi
- h. RVSWI (mmHg L m^-2)
- i. SVR (dynes/sec/cm^5)
- j. PVR (dynes/sec/cm^5)
- k. SBP/DBP/MAP
- l. API
- m. Standing weight
- n. Urine output
- o. Blood glucose taken from BMP
- p. HbA1c
- q. Current Vasoactive doses
- r. Renal function (serum Creatinine, serum eGFR)
- s. Total diuretic dose

**(6) Hour 51 & Hour 75 - if vasoactives are still required and pulmonary artery catheter is still being used for routine clinical care**, we will continue SGLT2i for up to 4 doses, and the additional invasive hemodynamics repeated two hours after each dose will be collected.

- a. Cardiac index (L/min/m^2)
- b. RAP (mmHg)
- c. PASP (mmHg)
- d. mPA (mmHg)
- e. PADP (mmHg)
- f. PCWP (mmHg)
- g. PAPi
- h. RVSWI (mmHg L m^-2)
- i. SVR (dynes/sec/cm^5)
- j. PVR (dynes/sec/cm^5)
- k. SBP/DBP/MAP
- l. API
- m. Standing weight
- n. Urine output
- o. Blood glucose taken from BMP
- p. HbA1c
- q. Current Vasoactive doses
- r. Renal function (serum Creatinine, serum eGFR)
- s. Total diuretic dose

Leveled invasive hemodynamic measurements, standing weights, intake and outputs, blood glucose, blood pressure, vasoactive doses, and renal function will stop being collected for the

study after the fourth dose of SGLT2i, or equivalent timing for those randomized to the No-SGLT2i arm.

The leveled hemodynamic measurements measured via a pulmonary artery catheter at end expiration will be collected. A picture will be taken and shown to an Advanced HF attending not involved with the patient's current care and blinded to treatment for interpretation.

The patient's participation in the study will end after completion of 4 doses of the SGLT2i or sooner if patient is transferred out of the CCU and continuous hemodynamic monitoring is discontinued, or if patient develops any of the safety end points as listed below. The physician will discuss the ongoing treatment plan with the patient at this point.

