## **Outcomes**

Primary outcome: Change in Indirect Fick cardiac index and change in PCWP

Secondary outcomes: changes in pulmonary artery pulsatility index (PAPi), Right atrial pressure (RAP), pulmonary artery systolic pressure (PASP), mean pulmonary artery pressure (mPA), pulmonary artery diastolic pressure (PADP), right ventricular stroke work index (RWSWI), systemic vascular resistance (SVR), pulmonary vascular resistance (PVR), mean arterial pressure (MAP), renal function, 24 hour urine output, changes in weight, changes in vasoactive dose, and blood glucose levels

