## **Safety End Points**

1. Need for initiation of second vasoactive medication and/or MAP < 60
2. Development of acute kidney injury, based on eGFR value < 30ml/min/1.73m^2
3. Adverse events reflecting urinary tract infection, genital infection, bone fracture, and diabetic ketoacidosis

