## **Study Subjects**

The study will include patients at UCMC who are admitted to the CCU by the advanced heart failure service after right heart catheterization for acute decompensated heart failure requiring vasoactive support.

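### No hour is named for the primary changes in CI and PCWP, while later readings are collected or dropped according to how patients respond after randomisation

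*Combined protocol and SAP*

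**What the plan says.** - **Late readings.** In the Study Design section, item (6), doses 3 and 4 and the Hour 51 and Hour 75 readings happen "if vasoactives are still required and pulmonary artery catheter is still being used for routine clinical care". Both conditions must hold. Items (2), (4) and (5), for Hours 0, 3 and 27, carry no vasoactive condition.
- **End of collection.** Collection stops for the "study after the fourth dose of SGLT2i, or equivalent timing for those randomized to the No-SGLT2i arm".
- **End of participation.** The closing paragraph of the same section ends participation after four doses, "or sooner if patient is transferred out of the CCU and continuous hemodynamic monitoring is discontinued". The same sentence adds a second early exit: "or if patient develops any of the safety end points as listed below". These exits apply at any hour.
- **Safety End Points.** The first is "Need for initiation of second vasoactive medication and/or MAP < 60"; the second is an eGFR below 30.
- **Outcomes.** The primary outcome is "Change in Indirect Fick cardiac index and change in PCWP". No hour or summary rule is given. The sample-size sentence names no hour either, and the documents give no analysis model or rule for early exit.
- **Study Subjects.** Patients are admitted "for acute decompensated heart failure requiring vasoactive support". The Inclusion Criteria require catheter monitoring but do not mention vasoactives.
- **Source of data.** "All data points collected for use in this study are being measured as part of the patient's routine care".

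**The concern.** For a patient who enters on vasoactives, coming off them is a response after randomisation, and so is needing a second agent or falling below a MAP of 60. Followed as written, Hours 51 and 75 contain neither the patients weaned off support nor those who met a safety end point. Both exits are plausibly related to CI and PCWP, and both may differ by arm, because the rationale expects the drug to improve invasive hemodynamics. Treating physicians also know the assignment (Potential Risks).

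This would matter little if the primary result were tied to an hour before the selection starts. It is not. An analyst could use Hour 27, 51 or 75, or the last available reading, and still comply with the text. At stake is whether the primary comparison is between the groups that were randomised.

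**Working it through.** **1. The plan's own figures.** The inputs are 80% power, alpha 0.05 (two-sided assumed), 16 per arm for 5 mmHg and 18 per arm for 0.75 L/min/m². No SD is stated, so the sample sizes cannot be reproduced independently; the SD must be back-solved.
- Normal approximation, n = 2(SD × 2.80/δ)²: SD 5.0 mmHg gives 15.7, so 16; SD 0.80 gives 17.9, so 18. The figures are coherent with those SDs.
- Two-sample t-test: n = 18 needs a standardised difference of 0.961, so SD = 0.75/0.961 = 0.780. n = 16 needs 1.024, so SD = 5/1.024 = 4.88. These SDs are used below.

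**2. Selection model (all rates assumed).** The change Y is normal with SD σ and shifted by δ in the treated arm. A response index I has correlation ρ with Y. Patients with I above a cut-off c are weaned and lost, with c set so that a share w of controls is weaned. With λ(x) = φ(x)/Φ(x), the difference seen among those remaining is

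δ − ρσ[λ(c − ρδ/σ) − λ(c)].

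**3. Hour 51, weaning only.** Starting from 20 per arm:

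| ρ | w | λ(c) | λ(c − ρδ/σ) | CI difference (true 0.75) | PCWP difference (true 5) | Remaining, control/treated (CI case) |
|---|---|---|---|---|---|---|
| 0.3 | 20% | 0.350 | 0.482 | 0.72 | 4.8 | 16.0/14.2 |
| 0.5 | 40% | 0.644 | 0.948 | 0.63 | 4.2 | 12.0/8.2 |
| 0.7 | 60% | 0.966 | 1.466 | 0.48 | 3.2 | 8.0/3.5 |

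The λ columns are for CI. First row: 0.75 − 0.3 × 0.780 × (0.482 − 0.350) = 0.72. With ρ = 0 the difference stays at 0.75.

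**4. Hour 27, safety exits in one arm only.** If the share l with the lowest I leaves an arm, the mean of those remaining rises by ρσφ(z)/(1 − l), where z is the l-quantile. With ρ = 0.5:
- l = 10%: 0.5 × 0.780 × 0.195 = 0.076, giving 0.67 (controls exit) or 0.83 (treated exit).
- l = 20%: 0.5 × 0.780 × 0.350 = 0.137, giving 0.61 or 0.89.
- Equal 10% exits in both arms, or ρ = 0: 0.75.
- If 20% of treated patients exit from the other tail, those with the largest response: 0.75 − 0.137 = 0.61.

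**5. Hour 27, catheter lost early.** Applying the formula in step 2 with ρ = 0.5 and 10–30% of controls losing the catheter before Hour 27 gives 0.68–0.64, even if readings continue after safety end points.

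**6. Numbers.** By the normal approximation with SDs 5.0 and 0.80, 20 measured per arm gives power of 88.5% (PCWP) and 84.2% (CI). With 10 per arm remaining, it is 61% and 55%.

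**The case against.** The strongest reply is that every rate is assumed, the results fall on both sides of 0.75, and the firm defect is a single missing hour in a small pilot. Item (6) also calls the late readings additional, which suggests that they supplement the earlier set. Much of this stands. The figures are illustrations, and the wording does lean towards treating late readings as supplementary. But it does not fix the primary hour, and pilot status does not help when the trial is sized on these two outcomes.

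Three further points stand and limit the claim. Vasoactive support at entry rests on Study Subjects, not on the Inclusion Criteria; for anyone enrolled without it, failing the condition is not a response. Only a second agent or a low MAP triggers the hemodynamic exit, so a patient whose existing agent is increased remains. And Hour 27 is not clean either, because early transfer or catheter removal can select patients before it.

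Two stronger readings are tempting:
- A reader might infer from the listed genital infections and creatinine increase that treated patients will exit more often and inflate the effect. The documents do not support this. They do not link infection to CI or PCWP, the renal end point is an eGFR threshold rather than a creatinine rise, and Potential Risks also credits the class with renal benefit. Step 4 shows that treated-only exits can raise, lower or leave the difference unchanged.
- A reader might infer that deleting the vasoactive condition would by itself restore the true late difference. That depends on how many weaned patients keep the catheter, which is not stated. With ρ = 0.7, w = 60% and half keeping it, the difference goes from 0.48 to 0.78, past 0.75.

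**Conclusion.** The concern holds in this form: the stated rules remove routine-care readings according to response after randomisation, and nothing keeps those selected readings out of the primary result. The documents do not say that late readings will be used, only that they can be.

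Direction and size of bias are unknown. Under the assumed rates, the CI difference of 0.75 could appear as 0.72–0.48 at Hour 51 from weaning alone, and as about 0.61–0.89 at Hour 27 from one-arm safety exits. It stays at 0.75 if exit is unrelated to CI. These ranges rest on normal changes, back-solved SDs and correlations of 0.3–0.7. The textual finding does not depend on them. The sponsor should make the change; confidence is moderate because weaning and exit rates are not given.

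**What to change.** 1. **Outcomes.** Name change from Hour 0 to Hour 27, in all randomised patients, as the primary comparison for CI and PCWP. Report Hours 51 and 75 as supportive, with numbers remaining by arm.
2. **Item (6) and the end-of-participation paragraph.** Separate drug from data: a safety end point stops study drug but not data collection. Collect Hour 27, 51 and 75 readings in every randomised patient whose catheter is still in routine use, whatever the vasoactive status. Whether weaned patients receive doses 3 and 4 remains the sponsor's choice.
3. **Missing Hour 27 readings.** Because transfer or catheter removal can still select patients, record the reason for each missing reading and report the missing readings by arm. Add a sensitivity analysis, for example a baseline-adjusted repeated-measures model using Hours 0, 3 and 27.

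The cost is an amendment to those sections and slightly more abstraction of routine-care data. Consent wording on when collection stops may also need to change. No patients, procedures or catheter time are added.

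### Safety events are observed for a time that depends on the patient's clinical course, and no common window is set for comparing the arms

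*Combined protocol and SAP*

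**What the plan says.** All references are to the Combined protocol and SAP, mainly the section Study Design, Study Procedures, and Statistical Procedures.

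- **Start of exposure.** At Hour 1, "patients will be given SGLT2i if randomized to SGLT2i arm, or not given SGLT2i if randomized to no SGLT2i arm".
- **Last unconditional reading.** Hour 27, two hours after the second dose, "which will be administered 24 hours after first dose".
- **Later readings.** Hours 51 and 75 take place only "if vasoactives are still required and pulmonary artery catheter is still being used for routine clinical care". In that case "we will continue SGLT2i for up to 4 doses".
- **End of data collection.** Measurements stop for the "study after the fourth dose of SGLT2i, or equivalent timing for those randomized to the No-SGLT2i arm".
- **End of participation** (the paragraph just before Outcomes). After four doses, or "sooner if patient is transferred out of the CCU and continuous hemodynamic monitoring is discontinued". A safety event is a further trigger in the same sentence: "or if patient develops any of the safety end points as listed below".
- **Safety End Points.** Item 1 is "Need for initiation of second vasoactive medication and/or MAP < 60". Item 2 is an eGFR below 30. Item 3 covers infections, fracture and ketoacidosis. The section gives no observation window, no follow-up after CCU exit, and no choice between proportion, rate and time to event.

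The Data and Safety Monitoring section adds only that follow-up lasts under four days, that patients are closely monitored in the CCU, and how events are reported.

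**The concern.** The length of time for which a patient can contribute a safety event is decided by how the patient does. One who is weaned and transferred stops contributing; one who stays on vasoactives with a catheter contributes for up to three days. The trial's hypothesis is that SGLT2i improves haemodynamics during the ICU stay, so the treatment could itself change when observation ends. Care is also open-label: the treating physician is told the assignment and may override it (Potential Risks), so knowledge of the arm could affect how long monitoring goes on, in either direction.

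If length of stay does differ by arm, counting events during participation compares the arms over different amounts of time. The arm that leaves sooner has fewer hours in which an event can be recorded.

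A second loss comes from the same paragraph. Because a first safety end point ends participation, a later event of another type in that patient is not captured. An eGFR fall below 30 that follows a hypotensive episode is an example.

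**Working it through.** The documents give no safety event rate, exit pattern or safety calculation, so there is no planned figure to reproduce. The first step below is arithmetic on the schedule. The rest is illustration on stated assumptions.

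**1. Hours at risk after the first dose**

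- To Hour 27: 27 − 1 = 26 h.
- To the fourth dose: doses fall at Hours 1, 25, 49 and 73, so 73 − 1 = 72 h.
- To the Hour 75 reading: 75 − 1 = 74 h. Hour 75 is 75/24 = 3.1 days, which agrees with follow-up of under four days.
- Ratio: 74/26 = 2.8.
- Minimum: none stated. Transfer before Hour 27 is allowed, so 26 h is the scheduled lower value and not a floor.

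**2. Illustration with the same true hazard in both arms**

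Assumptions, not from the documents: constant hourly hazard h; a share e of the arm observed for 26 h and the rest for 74 h; e = 0.6 in one arm and 0.3 in the other.

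Crude proportion = e(1 − exp(−26h)) + (1 − e)(1 − exp(−74h))

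At h = 0.01 the two risks are 1 − exp(−0.26) = 22.9% and 1 − exp(−0.74) = 52.3%. Hence 0.6 × 22.9 + 0.4 × 52.3 = 34.7%, and 0.3 × 22.9 + 0.7 × 52.3 = 43.5%.

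| h per hour | e = 0.6 | e = 0.3 |
|---|---|---|
| 0.01 | 34.7% | 43.5% |
| 0.005 | 19.7% | 25.3% |
| 0.002 | 8.5% | 11.1% |

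With 72 h in place of 74 h, the first row becomes 34.3% v 42.8%, so the choice of upper end hardly matters. At a control-arm hazard of 0.01, a true hazard ratio of 1.37 against the early-leaving arm would show as equal proportions.

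**3. A milder assumed split**

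Let one arm leave 70/20/10% at 26/50/74 h (mean 35.6 h) and the other 30/30/40% (mean 52.4 h), with equal hazard. If the 74 h risk is 20%, the crude proportions are 10.1% v 14.5%. Over 74 h risks from 5% to 40%, the apparent risk ratio is 0.68 to 0.72 with no true difference.

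**4. If the hazard falls after exit**

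Take h = 0.01 in the CCU and e = 0.6 v 0.3, and ask what complete follow-up of everyone to 74 h would show. The count during participation is 34.7% v 43.5% in every row, a gap of 8.8 points.

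| Hazard after exit | Complete follow-up | True gap | Artefact |
|---|---|---|---|
| Unchanged | 52.3% v 52.3% | 0 | 8.8 points |
| One quarter | 39.9% v 46.1% | 6.2 points | 2.6 points |
| Zero | 34.7% v 43.5% | 8.8 points | 0 |

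For the middle row, an early leaver's risk is 1 − exp(−(0.26 + 48 × 0.0025)) = 31.6%.

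**5. Against sampling error**

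With 20 per arm, the standard error of the difference is √[(0.347 × 0.653 + 0.435 × 0.565)/20] = 15 points at h = 0.01 and √[(0.085 × 0.915 + 0.111 × 0.889)/20] = 9 points at h = 0.002. The gaps of 8.8 and 2.6 points are 1.8 and 0.5 patients of 20.

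**The case against.** The strongest reply is that the documents do not contain the analysis at fault. Nothing says that safety events will be compared between arms as crude proportions, or compared at all. The only stated use of the safety end points is to end participation. That is right, and the point is therefore an observation rule without a common window or analysis, not a wrong analysis written into the plan.

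A reader might also infer that an arm leaving the CCU sooner will look safer than it is. The documents do not support this. They give no exit data, so unequal stay is only a possibility. The inference also needs risk to persist after exit. A patient weaned from support probably has little risk of needing a second vasoactive, and with zero risk after exit the artefact vanishes (step 4). This weakens the concern most for end point 1. It protects less against a later eGFR below 30.

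Nor is this the trial's only source of safety information by arm. MAP, renal function and change in vasoactive dose are secondary outcomes, scheduled at Hours 3 and 27 in both arms without the Hour 51/75 condition. They are readings at fixed times and do not replace event counts, but they cover the same physiology.

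Finally, in a pilot of 40 the artefact is smaller than chance variation. That stands and limits the weight of the point. Unlike chance error, though, a systematic one would carry over if these data were pooled or used to plan a larger trial.

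**Conclusion.** The point holds as a gap worth closing at low cost. By the plan's own rules, time at risk for end points 1 and 2 depends on clinical course: about 26 h to 72–74 h after the first dose on schedule, with no minimum. No common window corrects for this, and events after a first safety end point are not captured.

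Whether the arm comparison would be biased depends on length of stay differing by arm, which the hypothesis and the open-label care make possible but the documents do not establish. The illustrative gap, 34.7% v 43.5% at 0.01 per hour and 8.5% v 11.1% at 0.002 per hour, rests on an assumed 60% v 30% exit split and an equal, constant hazard that continues after exit. It falls towards no bias as risk after exit nears zero. It is secondary to the imprecision of 20 patients per arm.

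**What to change.** Amend two places together, since a new analysis rule has no effect if data collection has already stopped.

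1. **End-of-participation paragraph.** State that safety data collection, as distinct from treatment, continues from the routine chart for every randomised patient from Hour 1 to Hour 27, regardless of CCU exit, catheter removal or an earlier safety event. No dose or clinical rule changes.
2. **Safety End Points.** State that end points 1 and 2 are compared between arms over Hour 1 to Hour 27.
3. **Hour 27 to Hour 75.** Report separately and descriptively, with hours at risk by arm, and note that exit in this period depends on response. Do not pool it with the common window into one proportion.

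The cost is two short text changes and a little chart abstraction for patients who leave or have an event before Hour 27. The common window will hold fewer events than the full stay. It equalises time but not intensity of measurement, since blood pressure and creatinine may be recorded less often after CCU exit; the report should say how many patients this affects in each arm.
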